5. STUDY PROCEDURES

5.1. Screening

A signed ICF will be obtained from each patient prior to performing any study-specific procedures. A copy of the ICF will be retained in the study file and a copy will be provided to the patient.

The following screening procedures will be performed for all potential patients at a visit conducted within 14 days of study entry:

1. Demographic data
2. Medical history, including review of concomitant medications, tobacco and alcohol usage
3. Review of inclusion/exclusion criteria
4. Height, body weight, and calculation of body mass index (BMI)
5. Routine physical examination
6. Neurological examination
7. 12-lead ECG
8. Vital signs, including temperature, heart rate, blood pressure, and respiratory rate measured after the patient has been resting for at least 3 minutes
9. Clinical laboratory evaluations, including complete blood count (CBC) and white blood cells (WBC) with differential, serum chemistries, cystatin C, urinalysis (UA), and thyroid stimulating hormone (TSH)
10. Pregnancy test for all females of childbearing potential
11. SVC
12. Muscle strength measurements
13. ALSFRS-R
14. Voice recording
15. Fine motor measurement of handwriting and tracing of forms via an app (if the device is suitable for use in that region)
16. Ashworth score
17. ALSAQ-5
18. Beck Depression Inventory-Fast Screen (BDI-Fast Screen)

Once a patient is confirmed eligible to participate and before the first dose on Day 1, patients will be randomized to receive either CK-2127107 or placebo.

5.2. First Dosing Day (Day 1)

Prior to study drug dosing on Day 1, the following procedures will be performed:

1. Vital signs, including heart rate, blood pressure, and respiratory rate measured after the patient has been resting for at least 3 minutes
2. Weight and calculation of BMI
3. Clinical laboratory evaluations, including CBC and WBC with differential, serum chemistries, cystatin C and UA
4. PK blood sample
5. SVC
6. Muscle strength measurements
7. ALSFRS-R
8. Voice recording
9. Fine motor measurement of handwriting and tracing of forms via an app (if the device is suitable for use in that region)
10. Ashworth score
11. Falls assessment
12. ALSAQ-5
13. Record Health Economic Outcomes Measures
14. AE/SAE evaluation and concomitant medication assessment (since last visit)
15. BDI-Fast Screen

Patients will receive their first dose of study drug (CK-2127107 or placebo) within 2 hours of a meal.

The following assessment will be performed after the first dose of study drug is given:

16. PK blood sample at 1 hour post-dose

Training will also be provided to the patient for the measurements patients will perform at home.

- For patients who have access to a mobile device, the application will be downloaded to the device and instructions provided as detailed in the study manual on recording voice.
- All patients will be trained in performing SVC using a portable spirometer (if the device is suitable for use in that region) as detailed in the study manual.

Home voice recordings and SVC testing will be performed by the patient weekly for the duration of the study following Day 1.

Patients will be given an adequate supply of study drug (CK-2127107 or placebo) to take twice daily for 4 weeks. A dosing diary will be provided for patients to record the date and time of twice daily study drug administration.

5.3. Week 2 Visit

Prior to study drug dosing at the Week 2 Visit, the following procedures will be performed:

1. Vital signs, including heart rate, blood pressure, and respiratory rate measured after the patient has been resting for at least 3 minutes
2. Weight and calculation of BMI
3. PK blood sample
4. Clinical laboratory evaluations, including CBC and WBC with differential, serum chemistries, cystatin C and UA
5. SVC
6. Muscle strength measurements
7. ALSFRS-R
8. Voice recording
9. Fine motor measurement of handwriting and tracing of forms via an app (if the device is suitable for use in that region)
10. Ashworth score
11. Falls assessment
12. ALSAQ-5
13. Record Health Economic Outcomes Measures
14. AE/SAE evaluation and concomitant medication assessment (since last visit)
15. BDI-Fast Screen

Patients will receive their dose of study drug (CK-2127107 or placebo) within 2 hours of eating a meal. Patients should be reminded to bring their unused study drug with them to the clinic and that they will be taking their dose of study drug while at the clinic. The following assessment will be performed after the dose of study drug is given:

16. PK blood sample at 1 hour post-dose

Patients will have already been given their supply of study drug (CK-2127107 or placebo) to take twice daily at home until their next clinic visit at Week 4. A dosing diary will be provided for patients to record the date and time of twice daily study drug administration.

5.4. Week 4 Visit

Prior to study drug dosing at the Week 4 Visit, the following procedures will be performed:

1. 12-lead ECG
2. Vital signs, including heart rate, blood pressure, and respiratory rate measured after the patient has been resting for at least 3 minutes
3. Weight and calculation of BMI
4. PK blood sample
5. Clinical laboratory evaluations, including CBC and WBC with differential, serum chemistries, cystatin C and UA

6. SVC
7. Muscle strength measurements
8. ALSFRS-R
9. Voice recording
10. Fine motor measurement of handwriting and tracing of forms via an app (if the device is suitable for use in that region)
11. Ashworth score
12. Falls assessment
13. ALSAQ-5
14. Record Health Economic Outcomes Measures
15. AE/SAE evaluation and concomitant medication assessment (since last visit)
16. BDI-Fast Screen

Patients will receive their dose of study drug (CK-2127107 or placebo) within 2 hours of eating a meal.

Patients will be given an adequate supply of study drug (CK-2127107 or placebo) to take twice daily for 4 weeks at home until their next clinic visit at Week 8. A dosing diary will be provided for patients to record the date and time of twice daily study drug administration.

5.5. Week 8 Visit

Prior to study drug dosing at the Week 8 Visit, the following procedures will be performed:

1. Vital signs, including heart rate, blood pressure, and respiratory rate measured after the patient has been resting for at least 3 minutes
2. Weight and calculation of BMI
3. PK blood sample
4. SVC
5. Muscle strength measurements
6. ALSFRS-R
7. Voice recording
8. Fine motor measurement of handwriting and tracing of forms via an app (if the device is suitable for use in that region)
9. Ashworth score
10. Falls assessment
11. ALSAQ-5
12. Record Health Economic Outcomes Measures
13. AE/SAE evaluation and concomitant medication assessment (since last visit)

14. BDI-Fast Screen

Patients will receive their dose of study drug (CK-2127107 or placebo) within 2 hours of eating a meal.

Patients will be given an adequate supply of study drug (CK-2127107 or placebo) to take twice daily for 4 weeks at home. A dosing diary will be provided for patients to record the date and time of twice daily study drug administration.

5.6. Week 12 Visit

Prior to the last dose of study drug at the Week 12 Visit, the following procedures will be performed:

1. Vital signs, including heart rate, blood pressure, and respiratory rate measured after the patient has been resting for at least 3 minutes
2. Weight and calculation of BMI
3. PK blood sample
4. Clinical laboratory evaluations, including CBC and WBC with differential, serum chemistries, cystatin C and UA
5. SVC
6. Muscle strength measurements
7. ALSFRS-R
8. Voice recording
9. Fine motor measurement of handwriting and tracing of forms via an app (if the device is suitable for use in that region)
10. Ashworth score
11. Falls assessment
12. ALSAQ-5
13. Record Health Economic Outcomes Measures
14. AE/SAE evaluation and concomitant medication assessment (since last visit)
15. BDI-Fast Screen

Patients will receive their dose of study drug (CK-2127107 or placebo) within 2 hours of eating a meal. The following assessment will be performed after the last dose of study drug is given:

16. PK blood sample at 1 hour post-dose

5.7. Follow-Up Visit

The following procedures will be performed at a Follow-Up Visit 4 weeks after each patient's final dose of study drug:

1. 12-lead ECG

2. Vital signs including heart rate, blood pressure, and respiratory rate measured after the patient has been resting for at least 3 minutes
3. Weight and calculation of BMI
4. Abbreviated physical examination
5. Neurological examination
6. Clinical laboratory evaluations, including CBC and WBC with differential, serum chemistries, cystatin C, UA, and TSH
7. Pregnancy test for all females of childbearing potential
8. SVC
9. Muscle strength measurements
10. ALSFRS-R
11. Voice recording
12. Fine motor measurement of handwriting and tracing of forms via an app (if the device is suitable for use in that region)
13. Ashworth score
14. Falls assessment
15. ALSAQ-5
16. Record Health Economic Outcomes Measures
17. AE/SAE evaluation and concomitant medication assessment (since last visit)
18. BDI-Fast Screen

5.8. Early Termination Visit

If a patient decides to terminate early from the study, they should be seen in the clinic as soon as possible following discontinuation of study drug. The following procedures will be performed:

1. 12-lead ECG
2. Vital signs including heart rate, blood pressure, and respiratory rate measured after the patient has been resting for at least 3 minutes
3. Weight
4. Abbreviated physical examination
5. Neurological examination
6. Clinical laboratory evaluations, including CBC and WBC with differential, serum chemistries, cystatin C and UA
7. SVC
8. Muscle strength measurements
9. ALSFRS-R

10. Voice recording
11. Fine motor measurement of handwriting and tracing of forms via an app (if the device is suitable for use in that region)
12. Ashworth score
13. Falls assessment
14. ALSAQ-5
15. Record Health Economic Outcomes Measures
16. AE/SAE evaluation and concomitant medication assessment (since last visit)
17. BDI-Fast Screen

If a patient decides to terminate early from the study but does not wish to return to the clinic for an Early Termination Visit, they should be contacted by phone whenever possible and the following information should be collected:

1. ALSFRS-R
2. ALSAQ-5
3. Record Health Economic Outcomes Measures
4. Falls Assessment
5. AE/SAE evaluation and concomitant medication assessment (since last visit)

5.9. Visit Windows

To aid in scheduling patient visits, the following study visit windows are considered acceptable (Table 2). If a patient visit must be scheduled outside the visit window, the Medical Monitor should be contacted.

Table 2: Visit Windows

Visit	Visit Window
Screening	Up to 14 days prior to Day 1 visit (as per protocol)
Day 1	First day of randomized, double-blind dosing
Week 2 (Day 15)	± 2 days
Week 4 (Day 29)	± 2 days
Week 8 (Day 57)	± 4 days
Week 12 (Day 85)	± 4 days
Follow-Up	4 weeks after last dose of study drug ± 4 days

5.10. Diet Control

All doses of study drug should be taken within 2 hours following a meal.

Subjects will abstain from consuming grapefruit and Seville oranges along with foods or beverages containing them from Day 1 through the Follow-Up visit.

5.11. Concomitant Medications

All prescription drugs, over-the-counter medications, nutraceuticals and herbal remedies taken by the patient from the time of screening through the Follow-Up visit should be entered into the electronic case report form (eCRF). Medications that strongly inhibit the activity of CYP3A4 should be avoided from 7 days before the start of dosing (Day 1) through the last day of dosing (End of Week 8). Medications that strongly induce the activity of CYP3A4 should be avoided from 14 days before the start of dosing (Day 1) through the last day of dosing (Week 12). Please refer to [Appendix B](#) for strong inhibitors and inducers of CYP3A4. Medications that are OCT1/OCT2 substrates should be avoided from 7 days before the start of dosing or used with caution during the trial, as CK-2127107 may have the potential to inhibit OCT1 and OCT2-mediated transport. Please refer to [Appendix B](#) for OCT1/OCT2 substrates that should be avoided or used with caution.

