5.13. Clinical Safety Assessments

5.13.1. Clinical Laboratory Evaluations

Clinical laboratory evaluations will be collected at Screening, Day 1, Week 2 visit, Week 4 visit, Week 12 visit, and at the Follow-Up Visit as described in [Appendix D](#).

5.13.2. 12-Lead Electrocardiograms

A 12-lead ECG, including ECG parameters of RR, PR, QRS, QT and QTc intervals as well as significant findings will be obtained at Screening, Week 4 visit, and at the Follow-Up Visit.

When 12-lead ECGs are scheduled at the same time as blood draws, the order of evaluation will be ECG, vital signs, and then blood draw.

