5.4.3. Pharmacokinetics Analysis Set

The Pharmacokinetics Analysis Set (PKS) will consist of all randomized patients who have at least one evaluable plasma concentration of reldesemtiv, provided they have no major protocol violations that could affect the PK results of reldesemtiv.

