8.3. Concomitant and Other Medications

Concomitant medications reported on the eCRF will be summarized for the safety analysis set. See [Section 5.5.10.4](#) for the definition of concomitant medications. Medications with a start date that is 28 days after the last dose of the study drug will be excluded from the summary. The World Health Organization Drug dictionary will be used to classify medications by therapeutic class (ATC Class 3) and preferred name. If ATC Class 3 is not available, ATC Class 2 will be used in the summary. Coding will be performed using WHO Drug Dictionary Enhanced with Herbal Dictionary, B2, March 2017.

The number and percentage of patients who received concomitant medication will be summarized by dose level, therapeutic class and preferred term (using ATC Class Level III). Multiple drug usage by a patient will be counted only once in each category.

CYP3A4 strong inhibitors that should be avoided from 7 days before the start of dosing through the last day of dosing. CYP3A4 strong inducers that should be avoided from 14 days before the start of dosing through the last day of dosing. OCT1/OCT2 substrates that should be avoided from 7 days before the start of dosing or should be used with caution during the trial. Patients who take CYP3A4 strong inhibitors, CYP3A4 strong inducers, or OCT1/OCT2 substrates prior or during the study treatment will be listed.

In addition, a listing of concomitant medication with start/stop date, days relative to the start of therapy, dose / unit / route / frequency, indication and purpose of all medications taken from screening through the end of study will be provided.

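### Protocol Section 5.11 mislabels the last day of dosing as the end of Week 8 in the strong CYP3A4 inhibitor restriction; it should say Week 12 (minor)

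*Protocol*

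**What the plan says.** Protocol Section 5.11 sets two restrictions with the same verbal end point. Strong CYP3A4 inhibitors are to be avoided from 7 days before Day 1 "through the last day of dosing (End of Week 8"). Strong CYP3A4 inducers are to be avoided from 14 days before Day 1 "through the last day of dosing (Week 12").

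The rest of the protocol places the last dose as follows:

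- Table 1 (Section 3.1) gives 12 weeks of dosing in all four arms.
- At the Week 8 Visit (Section 5.5) patients receive drug "to take twice daily for 4 weeks at home. A dosing diary will be provided".
- Section 5.6 opens its list of procedures with "Prior to the last dose of study drug at the Week 12 Visit".
- Table 2 (Section 5.9) puts the Week 8 Visit on Day 57 and the Week 12 Visit on Day 85, each with a window of 4 days either side.

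SAP Section 8.3 repeats the inhibitor rule without a week: "CYP3A4 strong inhibitors that should be avoided from 7 days before the start of dosing through the last day of dosing". It adds: "Patients who take CYP3A4 strong inhibitors, CYP3A4 strong inducers, or OCT1/OCT2 substrates prior or during the study treatment will be listed". SAP Section 5.4.3 admits patients with an evaluable concentration to the PK set, "provided they have no major protocol violations that could affect the PK results of reldesemtiv".

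**The concern.** The inhibitor sentence contradicts itself, because the last day of dosing is not at the end of Week 8. The text can therefore be applied in two ways. If the words govern, the restriction lasts as long as dosing does. If the stated week governs, it lapses at about the visit where sites hand out the final four weeks of drug.

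No other protocol text states an on-treatment end date for inhibitor drugs. Exclusion criterion 10 covers only the period before the first dose, and Appendix B marks strong inhibitors as drugs to avoid but gives no dates. The SAP wording is clear, but sites work from the protocol.

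Two things are at stake. One is the possible start of a strong inhibitor in a patient taking up to 900 mg/day. The other is the Week 12 concentrations. These enter the Week 12 riluzole plots (protocol Section 8.4.7), the concentration bins (SAP Section 5.5.12), and the steady-state regression and edaravone comparison (SAP Section 9.1).

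**Working it through.** **1. Which week is right.** A visit at week w falls on Day 7w + 1. This reproduces Table 2: Week 2 = Day 15, Week 4 = Day 29, Week 8 = Day 57, Week 12 = Day 85. The last dose is at the Week 12 Visit, so the last day of dosing is nominally 7 × 12 + 1 = Day 85. The label in the inhibitor sentence cannot be reproduced from the schedule; the label in the inducer sentence can.

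**2. Days left uncovered.**

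| Reading | Calculation | Uncovered days | Share of dosing days |
|---|---|---|---|
| The words govern (last day of dosing) | 85 − 85 | 0 | 0% |
| The stated week governs, taken as the Week 8 Visit (Day 57) | 85 − 57 | 28 (Days 58–85) | 28/85 = 32.9% |
| The stated week governs, taken as Day 56 | 85 − 56 | 29 (Days 57–85) | 29/85 = 34.1% |
| Visit windows, shortest gap (Week 8 on Day 61, Week 12 on Day 81) | 81 − 61 | 20 | 20/81 = 24.7% |
| Visit windows, longest gap (Week 8 on Day 53, Week 12 on Day 89) | 89 − 53 | 36 | 36/89 = 40.4% |

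**3. PK samples in the uncovered period, if the stated week governs.**

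- Current schedule (protocol Table 3): Day 1, Week 2, Week 4, Week 8 and Week 12 give 2 + 2 + 1 + 1 + 2 = 8 samples. Two of the 8 (25%) are at Week 12.
- Patients enrolled before Amendment 03 (SAP Section 9.1): Hours 0, 1 and 3 on Day 1, and Hours 0, 1, 3 and 6 at Weeks 2 and 12. Assuming one pre-dose sample each at Weeks 4 and 8, as now, the total is 3 + 4 + 1 + 1 + 4 = 13. Four of the 13 (31%) are at Week 12.
- Trough visits that feed the concentration bins are Weeks 2, 4, 8 and 12. One of the 4 is affected.

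**4. Which inhibitors are concerned.** Appendix B lists nine strong inhibitors, two of them foods (grapefruit and Seville oranges). Section 5.10 bars both foods from Day 1 through the Follow-Up visit, so the gap can concern only the seven drugs.

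**5. How late a correction comes.** The pooled-site counts in SAP Appendix C sum to 20 + 53 + 49 + 52 + 61 + 71 + 51 + 36 + 65 = 458 FAS patients, against a target of about 445. Group 8 is summed from its sites: 10 + 3 + 3 + 5 + 10 + 5 = 36. The SAP is dated 14 December 2018. A protocol edit at that date could affect only patients who had not yet taken their last dose; the documents do not say how many there were.

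**The case against.** The strongest reply is that the text largely corrects itself. The governing words name the last day of dosing and the week is only a label on it. To take the label literally, a site would have to treat Week 8 as the end of dosing while dispensing four more weeks of drug, and disregard the next sentence. It would also make little sense to bar grapefruit through Follow-Up yet release ketoconazole at Week 8. The rule is worded as something to avoid, and Section 5.15, item d, separately allows discontinuation for non-permitted medication that might affect safety or assessments. SAP Section 8.3 lists strong-inhibitor users on treatment in any case. All of this stands, and it makes zero uncovered days the better-supported reading. It does not make the label correct.

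Three stronger inferences are tempting, and the documents do not support them:

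- **That the error creates a gap in safety monitoring.** Section 5.13.1 reads "Clinical laboratory evaluations will be collected at Screening, Day 1, Week 2 visit, Week 4 visit, Week 12 visit", so no safety laboratory visit is scheduled between Day 29 and Day 85 under either reading. Correcting the label would not change that.
- **That PK-set membership is undefined because of this error.** SAP Section 6.3 gives no criteria to separate major from minor deviations, but that is a separate matter and the criteria may sit in another document. The SAP's own statement of the inhibitor rule already runs to the last day of dosing.
- **That Week 12 exposure will be distorted.** The documents give neither the size of an interaction with a strong inhibitor nor the expected use of such drugs, so no effect on concentrations can be calculated.

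**Conclusion.** The label is wrong and the point holds as a minor one. The inhibitor restriction should end at the last dose at Week 12, nominally Day 85. The likeliest consequence is none.

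The 28 of 85 dosing days (33%; 25% to 40% across the visit windows) is a conditional worst case. It assumes that a site follows the stated week and takes it as the Week 8 Visit, and it applies to inhibitor drugs only. Under that assumption the Week 12 PK samples fall outside the restriction: 2 of 8 on the current schedule, 4 of 13 for patients enrolled before Amendment 03. The 13 rests on the assumption that Weeks 4 and 8 had one sample each before that amendment.

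A reader might infer that the efficacy result is at risk. It is not: FAS membership does not depend on concomitant medication, and neither the sample size calculation nor the primary SVC model uses this rule.

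**What to change.** In protocol Section 5.11, change the parenthetical in the strong-inhibitor sentence from End of Week 8 to Week 12, so that it matches the inducer sentence and SAP Section 8.3. When strong-inhibitor use is classified as a deviation for the PK set (SAP Sections 5.4.3 and 6.3), apply the Week 12 end date and find users from the SAP Section 8.3 listing. The diet, eligibility and PK sampling rules need no change.

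The text change is one phrase, but it needs the approvals in protocol Section 9.1: the sponsor, the investigator, the ethics bodies and, where applicable, the regulators. Given the enrolment in SAP Appendix C, its benefit for conduct may be small. The classification line needs no new data, because concomitant medications are already entered in the eCRF. It applies to every patient and should be settled before database lock.

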5.12. Pharmacokinetic Sampling

Blood samples for analysis of CK-2127107, its metabolites, and riluzole will be collected from patients at the nominal time points listed in [Table 3](#).

Table 3: Pharmacokinetic (PK) Samples

Day	Sample Time Points
Day 1	Pre-dose and 1 (\pm 15 min) hour post-dose
Week 2	Pre-dose and 1 (\pm 15 min) hour post-dose
Week 4	Pre-dose
Week 8	Pre-dose
Week 12	Pre-dose and 1 (\pm 15 min) hour post-dose

If an indwelling catheter is used, saline flushes will be used. In some cases, sites may be unable to obtain the 6 hour timepoint at Week 2 or Week 12 for logistical reasons; these cases should be discussed with the medical monitor preferably ahead of time.

After completion of bioanalysis, remaining plasma samples will be retained consistent with the Sponsor's standard operating procedures. These samples will not be used for pharmacogenomic testing.

